4.7 Characterization and assessment of risk factors

The following potential confounders and/or effect modifiers will be ascertained:

Demographics; Age at index date (20-39, 40-49, 50-64, 65-74 and 75-84 years), sex and calendar year of index date (2005-2006, 2007-2008 and 2009-2011). We will also calculate the time interval between start date and index date and subsequently categorize it into 5 time periods: first month; 2 to 6 months; 7 to 12 months; 1 to 2 years and longer than 2 years. This variable can be considered as adjustment/proxy for time to event. Socioeconomic status will be computed with the Townsend score.

Life style factors; Body mass index (calculated from recorded height and weight; weight in kg / (height in metres²) will be ascertained prior to index date. Standard cut points used to classify subjects are: underweight (BMI less than 20), normal weight (BMI 20-25), overweight (BMI 25 to 29) and obese (BMI \geq 30 kg/m²). Smoking status will be categorized into current smoker, past smoker, never smoker. Missing data will be assessed as a separate category. Most recent value before index date will be ascertained.

Comorbidity; Diabetes, coronary heart disease (MI, unstable angina or angina), cerebrovascular disease (ischaemic or haemorrhagic), epilepsy, seizure, COPD, GERD, and peptic ulcer antecedents (which includes dyspepsia, gastritis, uncomplicated peptic ulcer and complicated peptic ulcer), bipolar disorder, anxiety, depression, neuralgia/neuralgic pain, polyneuropathy/peripheral neuropathy, migraine, autoimmune disorders, CNS infections, cerebral trauma, hypertensive encephalopathy, eclampsia, mental retardation, cerebral palsy, dementia. Comorbidity will be ascertained prior to index date.

Comedication; Antiepileptic drugs, anxiolytics, hypnotics, antibiotics, antihypertensives (e.g. diuretics, beta-blockers...), antihistamines, antidepressants, statins, antidiabetics, nitrates, clopidogrel, low-dose ASA, NSAIDs, oral corticosteroids, oral anticoagulants. We will also collect information on polypharmacy: number of prescribed different drugs in the 30 days prior to the index date (0, 1-2, 3-5, 6-9, 10 or more). Comedication will be ascertained prior to index date.

Health care utilization: Number of GP visits, referrals and hospitalizations the year prior to index date.

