Drugs associated with the development of convulsion/seizure include cocaine, other CNS stimulants, cyclosporine, tacrolimus, pentylenetetrazole, picrotoxin, strychnine. There are also drugs, described to lower seizure threshold such as aminophylline, antidepressants, sedating antihistamines, antimalarial drugs, some antipsychotics (eg, clozapine), buspirone, fluoroquinolones, theophylline (Ruffman et al 2006). In a study from 1977, seizures were recorded in less than 1% of 32 812 consecutive patients prospectively monitored for drug toxicity in selected medical wards (Porter et Jick 1977).

Antiepileptic medications are a heterogeneous pharmacologic class characterized by various chemical structures and postulated mechanisms of actions (Paterno et al, 2010). The main therapeutic applications of antiepileptics include epilepsy, bipolar disorder, depression, neuralgia, and migraine (Ettinger et al, 2007). Antiepileptic drugs (AEDs) are among the most commonly prescribed centrally active agents. In a survey, carried out in a Danish County, 1.1% of the studied people received AEDs. The use of these drugs increased with increasing age (Rochat et al 2001).

Proton pump inhibitors (PPIs) and H₂-receptor antagonists (H₂RAs) are widely prescribed acid-suppressive medications that in general have good safety profiles (Yang and Metz, 2010). AstraZeneca has received spontaneous reports of convulsion/seizure reported in patients taking esomeprazole and omeprazole. As commonly observed in postmarketing reports, information with regard to possible underlying cause, concomitant medication and potentially contributing factors were limited. In AstraZeneca placebo-controlled studies comprising esomeprazole or omeprazole no reports of convulsion/ seizure in patients given PPIs were found.

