4.2 Source population

THIN is a computerized medical research database that contains systematically recorded data on more than 3 million UK primary care patients. It is representative of this population with regard to age, sex, and geographic distribution, and has been validated for use in pharmacoepidemiological research in multiple studies (Lewis et al 2007). Participating primary care practitioners (PCPs) record data as part of their routine patient

care, including demographics and life style factors (e.g. alcohol use, body mass index (BMI) and smoking status), consultation rates, referrals, hospital admissions, laboratory test results, diagnoses, prescriptions ordered by the PCPs, and a free text section, and send their data anonymously to THIN for use in research projects. Prescriptions issued by PCPs are recorded automatically in the database. The Read classification is used to code specific diagnoses (Stuart-Buttle et al 1996), and a drug dictionary based on data from the MULTILEX classification is used to code drug prescriptions (First Data Bank 2010).

The rationale for selection of THIN is the unique attributes of primary care databases in the UK (e.g. GPRD, Qresearch) for pharmacoepidemiological research. As GPRD and THIN are basically equivalent, we chose the database our research group has greater experience.

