4.8 Exposure definition

We will categorize medication use in the nested case-control analysis as follows: *current use* when the supply of the most recent prescription lasted until the index date; *recent use*, when the supply of the most recent prescription ended 1–90 days before the index date; *past use*, when the supply of the most recent prescription ended 91–365 days before the index date; and non-use, when there was no recorded use of the relevant medication in the 365 days before the index date.

Current users of PPI at index date will be further analyzed according to duration of treatment (continuous use on PPI therapy will be defined as the sequence of consecutive PPI Rx without presenting at least one break (gap of 30 days or greater between the end of supply and the start of supply of two consecutive Rx). Dose-response among current users of PPI will also be analyzed. Similar classification scheme will be applied to users of H₂RA.

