4.9 Statistical analysis

Incidence rate of seizure overall as well as age and sex-specific will be computed in the study cohort.

A nested case-control analysis will be performed to assess the effect of acid-suppressing drugs and potential risk factors for seizure using unconditional logistic regression. In this analysis all patients ascertained with an incident episode of seizures will be used as

cases. The control group will comprise a random sample of study cohort members, frequency-matched by calendar year (described in section 4.6). Under our study design of incidence density sampling, the odds ratio (OR) is an unbiased estimator of the incidence rate ratio (RR) (Rothman 2002).

To determine the association between study outcome and current use of PPI and H₂RA, we will run unconditional logistic regression models and compute the OR and their 95% confidence intervals (95%CI). The estimates will be adjusted for the frequency-matched variable (calendar year), age, sex, time to event and other independent risk factors described in section 4.7.

Sub-analyses will be repeated in the strata of individuals with epilepsy and individuals free of epilepsy for descriptive purposes.

Statistical analyses will be performed using Stata package version 11.0 (StataCorp LP, College Station, TX, USA).

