5. STUDY STRENGTHS AND LIMITATIONS

Strengths

A major strength of this study is that use of THIN enables analysis of an extensive sample of PPI users that is representative of the UK primary-care population, with a similar age and sex distribution to those in the national population supporting a broad external validity of our findings and generalizability. Also, we will analyze the risk in another drug class (H₂RA) that share similar treatment indication than PPI to verify the specificity of the results. Validation of the outcome with the PCP will help to reduce the extent of outcome misclassification when working with automated databases.

Limitations

A potential limitation of the study is that acid suppressing drug use could be misclassified in some instances. For example, the recording of a PPI prescription in THIN does not necessarily mean that the patient actually took the medication, although it is likely that patients with repeating prescriptions do take their medication as there is a prescription almost every month. Also, lack of recording of OTC acid suppressing drugs is another source of misclassification (PPI available as OTC June 2009 on UK market). This misclassification of drug exposure will most likely be non-differential and thus will bias the effect estimates towards the null. Therefore, it should be noted that to the extent

such misclassification occurs in our study population, our effect estimates will tend to underestimate the true risk. As with any medication, PPI users might differ from non-users in a number of characteristics, such as treatment indication, severity of the treatment indication, co-morbidity, etc. Like in all observational studies, there is always the possibility for some remaining confounding not amenable to adjust after all our efforts in the design and analyses.

Outcome missclassification of seizure will be substantially reduced with our two step validation process: first obtaining free text comments for the review of the patient profiles and second the direct validation with the PCP. The extent of recording of comorbidity, medication use and life style habits in THIN will help to minimize as much as possible potential confounding by any these variables.

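### The polypharmacy covariate in 4.7 does not exclude the PPI or H2RA under study, and 4.7 leaves out recorded alcohol use and several seizure-provoking drugs that the protocol names; the adjusted ORs may be biased

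*Protocol*

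**What the plan says.** Section 4.7 of the Protocol opens with "The following potential confounders and/or effect modifiers will be ascertained". Under comedication it adds "We will also collect information on polypharmacy", defined as the "number of prescribed different drugs in the 30 days prior to the index date (0, 1-2, 3-5, 6-9, 10 or more"). It does not say whether PPIs and H2RAs belong to the count.

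Section 4.9 adjusts the ORs for calendar year, age, sex, "time to event and other independent risk factors described in section 4.7".

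Section 4.8 defines current use as the case "when the supply of the most recent prescription lasted until the index date". Section 5 says of patients on repeat prescriptions that "there is a prescription almost every month".

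The Introduction (section 2) names drugs associated with seizures, among them CNS stimulants, cyclosporine and tacrolimus. It then names drugs "described to lower seizure threshold such as aminophylline, antidepressants, sedating antihistamines, antimalarial drugs, some antipsychotics (eg, clozapine), buspirone, fluoroquinolones, theophylline".

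Section 4.2 says that the database holds "life style factors (e.g. alcohol use, body mass index (BMI) and smoking status"). The life style item in 4.7 has BMI and smoking only.

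**The concern.** There are two separate problems with the covariate list.

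The first is the polypharmacy count. A current user with an acid-suppressant prescription in the 30-day window has at least one drug by virtue of being exposed, so cannot fall in the zero category. At each band edge the study drug lifts the user one category. Users are then compared, within a category, with non-users who on average take more other drugs. If seizure risk rises with the number of other drugs, this lowers the adjusted OR. In a safety study that is the direction that hides a risk.

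The second is a mismatch between what the protocol says matters or is recorded and what it plans to ascertain. Some drug classes that it names as seizure-provoking, and a life style factor that it names as available, do not reach the list from which the model is built. If they are related to acid-suppressant use, they leave residual confounding.

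**Working it through.** **The plan's own figure.** The only precision figure is in 4.9.1: an upper 95% limit of 1.48. With 100,000 person-years per group and 50 per 100,000, each group expects 50 events, so exp(1.96 × √(1/50 + 1/50)) = exp(0.392) = 1.48. It reproduces. It does not depend on the adjustment set, so no stated figure is wrong here.

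**Polypharmacy: inputs.** From the Protocol: the five categories, the 30-day window, the definition of current use, and near-monthly prescribing. All else is assumed: 8% current users, and a negative-binomial count of other drugs (dispersion 1, cut off at 40). Seizure risk depends on the number of other drugs only. I computed the expected logistic-regression OR twice, with the categories formed without and with the study drug.

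*Risk rising by category* (mean other drugs 1.5 in non-users, 4.5 in users, true OR 1.0):

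| Odds ratio per category | Study drug left out | Counted | Counted, 70% of users with a prescription in the window |
|---|---|---|---|
| 1.11 | 1.00 | 0.96 | 0.97 |
| 1.22 | 1.00 | 0.93 | 0.95 |
| 1.35 | 1.00 | 0.89 | 0.93 |
| 1.49 | 1.00 | 0.87 | 0.91 |

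*Risk rising per additional drug* (true OR 1.0):

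| Rate ratio per drug | Means, non-users / users | Left out | Counted | Counted ÷ left out |
|---|---|---|---|---|
| 1.05 | 2 / 3 | 1.01 | 0.96 | 0.95 |
| 1.05 | 2.5 / 5 | 1.03 | 0.99 | 0.96 |
| 1.10 | 2 / 3 | 1.02 | 0.93 | 0.91 |
| 1.10 | 2.5 / 5 | 1.09 | 1.01 | 0.92 |
| 1.20 | 2 / 3 | 1.07 | 0.90 | 0.84 |
| 1.20 | 1.5 / 4 | 1.16 | 0.99 | 0.85 |

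Over all 18 per-drug settings (true OR 1.0 and 1.5) the ratio in the last column runs from 0.84 to 0.96. At a true OR of 1.5, for example, 1.10 per drug with means 2 / 3 gives 1.52 left out and 1.39 counted. If only 75% of users have a prescription in the window, the ratio runs from 0.88 to 0.97. The absolute ORs at 1.20 per drug are sensitive to the cut-off at 40 drugs, so they should be read for the ratio only.

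The relative effect of counting the study drug is thus always downward. The net error is not: with 1.10 per drug and means 2.5 / 5, residual confounding inside the broad bands pushes the OR up and happens to cancel it (1.01 counted, 1.09 left out).

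**Drug lists side by side.** Of the drugs named in the Introduction, 4.7 covers antidepressants, antihistamines, buspirone (as an anxiolytic) and fluoroquinolones (within all antibiotics). It does not list antipsychotics, theophylline/aminophylline, antimalarials, cyclosporine/tacrolimus or CNS stimulants.

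**Omitted covariates: size.** Bias factor = (1 + p1(RR − 1)) / (1 + p0(RR − 1)), where p1 and p0 are the prevalences in users and non-users. All values are assumed.

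- Drug, RR 2, 3% v 1.5%: 1.03 / 1.015 = 1.015
- Drug, RR 3, 5% v 2%: 1.10 / 1.04 = 1.058
- Drug, RR 2, 1% v 1%: 1.01 / 1.01 = 1.00
- Heavier drinking, RR 2, 10% v 8%: 1.10 / 1.08 = 1.019
- Heavier drinking, RR 2, 6% v 8%: 1.06 / 1.08 = 0.981

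This set gives −2% to +6%. Stronger assumptions (drinking, RR 3, 10% v 5%) give 1.20 / 1.10 = 1.09.

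**The case against.** The protocol never says that the study drug is counted. The polypharmacy sentence stands under comedication, where no acid suppressant is listed, so a reader may take it to mean other drugs. The item is introduced as information to collect and reaches the model only through the general phrase in 4.9. An analysis plan could settle the point. This stands in part: the text is silent, and the finding is conditional on a literal reading. But the protocol fixes the variable, its window and its cut points, and a programmer who follows it as written would count the PPI.

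Part of the omitted information is covered in other ways. COPD, bipolar disorder, dementia and autoimmune disorders are listed comorbidities and partly stand in for the missing drug classes. Recorded drug abuse is excluded at entry (4.3.2) and ends follow-up (4.4). Recorded alcohol abuse and alcohol-related disease are handled likewise, and 4.5.1 excludes alcohol-related seizures. This stands too. What remains for alcohol is lower-level or unrecorded drinking.

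A reader might go further and infer that the adjusted ORs are biased, or that the result could not be interpreted. The documents do not support either. They give no prevalences or effect sizes, they do not show that the omitted factors go with acid-suppressant use, and the possible shifts can oppose each other. Section 5 also acknowledges residual confounding in general terms.

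**Conclusion.** The point holds as a defect in the definition of one covariate and an incomplete covariate list. It does not demonstrate bias.

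If polypharmacy enters the model and is programmed as worded, the adjusted OR falls by roughly 4-15% relative to a count without the study drugs. The size rests on the assumed drug counts and risk gradients. The net distance from the true OR may be smaller, because residual confounding within the broad bands can offset it. That would be chance cancellation and is no reason to keep the definition.

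The omitted drugs and alcohol use matter less: a few percent under most assumed inputs, and nothing if they are unrelated to acid-suppressant use. They are worth repairing because the protocol itself names these drugs as relevant and alcohol use as recorded. The change should be made before the analysis.

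**What to change.** In section 4.7:

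- Define polypharmacy as the number of different drugs prescribed in the 30 days before the index date, excluding all PPIs and H2RAs.
- Add antipsychotics, theophylline/aminophylline, antimalarials, cyclosporine/tacrolimus and CNS stimulants to comedication.
- Add the most recent recorded alcohol use before the index date to the life style factors, with a category for missing values.

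Separating fluoroquinolones from other antibiotics is optional.

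The change is to covariate wording. Section 4.2 describes prescriptions and alcohol use as recorded in the database, so no new data source is needed. The cost is a few more model terms, some of them for rarely used drugs, and some missing alcohol records.

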4.8 Exposure definition

We will categorize medication use in the nested case-control analysis as follows: *current use* when the supply of the most recent prescription lasted until the index date; *recent use*, when the supply of the most recent prescription ended 1–90 days before the index date; *past use*, when the supply of the most recent prescription ended 91–365 days before the index date; and non-use, when there was no recorded use of the relevant medication in the 365 days before the index date.

Current users of PPI at index date will be further analyzed according to duration of treatment (continuous use on PPI therapy will be defined as the sequence of consecutive PPI Rx without presenting at least one break (gap of 30 days or greater between the end of supply and the start of supply of two consecutive Rx). Dose-response among current users of PPI will also be analyzed. Similar classification scheme will be applied to users of H₂RA.

4.9 Statistical analysis

Incidence rate of seizure overall as well as age and sex-specific will be computed in the study cohort.

A nested case-control analysis will be performed to assess the effect of acid-suppressing drugs and potential risk factors for seizure using unconditional logistic regression. In this analysis all patients ascertained with an incident episode of seizures will be used as

cases. The control group will comprise a random sample of study cohort members, frequency-matched by calendar year (described in section 4.6). Under our study design of incidence density sampling, the odds ratio (OR) is an unbiased estimator of the incidence rate ratio (RR) (Rothman 2002).

To determine the association between study outcome and current use of PPI and H₂RA, we will run unconditional logistic regression models and compute the OR and their 95% confidence intervals (95%CI). The estimates will be adjusted for the frequency-matched variable (calendar year), age, sex, time to event and other independent risk factors described in section 4.7.

Sub-analyses will be repeated in the strata of individuals with epilepsy and individuals free of epilepsy for descriptive purposes.

Statistical analyses will be performed using Stata package version 11.0 (StataCorp LP, College Station, TX, USA).

4.9.1 Sample size

Assuming an experience of 100,000 person-years among PPI current users, 100,000 person-years among non users of PPI and an incidence rate of seizures of 50 per 100,000 person-years among non users of PPI and a true relative risk of one, a 95% CI would extend to 1.48 if the estimated ratio is 1. We expect to accumulate larger person-time experience than mentioned above both among current users of PPI and non users.

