4.6 Selection of Controls

A random series of controls, calendar-year-frequency matched to seizure cases will be sampled from the pooled study cohorts. This will be done by generating a random date within the study period for each study member. If the random date for a study member is included in the follow-up period, that person will be marked as an eligible control and the random date will be used as their index date. This method of selection of controls in nested case-control studies is known as "incidence density" sampling. The final size of the control sample will be determined by being at least four times the size of the final list of cases and be a round number.

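### The upper 95% limit of 1.48 in section 4.9.1 is the precision of a full-cohort rate ratio; the planned nested case-control odds ratio gives 1.55 at the minimum of four controls per case

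*Protocol*

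**What the plan says.** Section 4.9.1 (Sample size) of the protocol is the only place that states the precision of the study. Its inputs are person-time, "Assuming an experience of 100,000 person-years among PPI current users, 100,000 person-years among non users of PPI", and a rate, "an incidence rate of seizures of 50 per 100,000 person-years among non users of PPI". From these it concludes: "a true relative risk of one, a 95% CI would extend to 1.48 if the estimated ratio is 1". It then adds, without a figure, that more person-time is expected in both groups.

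The planned analysis is set out elsewhere. Section 4.9 says of the PPI and H2RA associations: "we will run unconditional logistic regression models and compute the OR". This is a nested case-control analysis. Section 4.6 fixes the number of controls only from below: "The final size of the control sample will be determined by being at least four times the size of the final list of cases". Controls are chosen by incidence density sampling. From the full cohort, section 4.9 plans incidence rates overall and by age and sex. It plans no cohort rate ratio for PPI.

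**The concern.** The precision statement uses person-years and a rate and has no term for the sampled controls. The planned estimator depends on those controls. Section 4.9 notes that under incidence density sampling the odds ratio estimates the incidence rate ratio without bias. That concerns the point estimate. It does not make the two standard errors equal, because a sample of controls measures the exposure distribution of the person-time with error, whereas a full cohort analysis knows it.

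This is a safety study whose final report is to go to the regulator (Table 3), and 1.48 is its only precision figure. A reader may take it as the size of risk that a null result would exclude. If the figure belongs to another analysis and errs in the favourable direction, that reader is somewhat misled.

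**Working it through.** **Inputs**

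- Person-years: 100,000 in PPI current users and 100,000 in non-users (4.9.1).
- Incidence in non-users: 50 per 100,000 person-years, so 50 expected cases (4.9.1).
- True and estimated ratio 1, so 50 expected cases in current users as well (4.9.1).
- Two-sided 95% interval, z = 1.96 (4.9).
- Controls per case: k, at least 4 (4.6). Under incidence density sampling, the exposure of controls follows person-time, so half of the controls are exposed on these inputs.

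**Step 1: reproduce the protocol's figure as a cohort rate ratio**

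SE(log RR) = √(1/50 + 1/50) = 0.200

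Upper limit = exp(1.96 × 0.200) = 1.480; lower limit = 0.676

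This matches 1.48. A one-sided 95% limit would be 1.39, and the exact conditional limit 1.51. So the stated figure is the ordinary two-sided Wald limit for the full cohort.

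**Step 2: the planned odds ratio on the same inputs, four controls per case**

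There are 100 cases (50 exposed, 50 not) and 400 controls (200 exposed, 200 not).

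SE(log OR) = √(1/50 + 1/50 + 1/200 + 1/200) = √0.05 = 0.2236

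Upper limit = exp(1.96 × 0.2236) = 1.550; lower limit = 0.645

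A logistic regression fitted to this 2×2 table gives the same interval, 0.645 to 1.550. The variance is 0.05 against 0.04, which is 25% larger.

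**Step 3: more controls per case**

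| Controls per case | SE(log OR) | Upper 95% limit |
|---|---|---|
| 4 | 0.2236 | 1.550 |
| 5 | 0.2191 | 1.536 |
| 10 | 0.2098 | 1.509 |
| 20 | 0.2049 | 1.494 |
| 50 | 0.2020 | 1.486 |
| no limit | 0.2000 | 1.480 |

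The full-cohort value is approached only as the ratio grows without bound.

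**Step 4: person-time that gives 1.48 at 4:1**

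With a and b cases in the two groups and a ratio of 1, the variance at 4:1 is 1.25 × (1/a + 1/b). It must equal 0.04.

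- Equal groups: 2.5/a = 0.04, so a = 62.5 cases, or 125,000 person-years, per group.
- PPI held at 100,000 person-years (a = 50): 1/b = 0.04/1.25 − 1/50 = 0.012, so b = 83.3 cases, or about 167,000 non-user person-years.

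Cases and controls who are recent or past users do not change this. When rates are equal, the ratio of controls to cases within the current-use and non-use groups stays at about 4:1 in expectation.

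**The case against.** The strongest reply is that nothing was miscalculated. Section 4.9.1 gives person-years and a rate, 1.48 follows exactly from them, and the text speaks of an estimated ratio without saying that it means the 4:1 odds ratio. It stands that the arithmetic is right. The fault is that the figure describes an analysis that the protocol does not plan for PPI.

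The second reply is that the scenario is a deliberate floor, because the section says that larger person-time is expected. Other parts agree. Section 4.5.2 draws 300 potential cases at random and refers to others remaining, against 100 cases in the scenario. Section 4.2 describes a database of more than 3 million patients. Unequal groups are also likely, since cohort members must be free of acid-suppressing drugs for a year at entry. If, purely as an assumption, non-users contributed 1,000,000 person-years and PPI users 100,000, the limit at 4:1 would be exp(1.96 × √(1.25 × (1/50 + 1/500))) = 1.38. This reply stands as to consequence: a reader who inferred that the study cannot reach 1.48, or is too small, would go beyond the documents. It does not remove the mismatch. The expected surplus is not quantified, and 1.48 is stated for 100,000 person-years per group.

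Third, four controls per case is a minimum. That also stands: 1.55 is the value at that minimum and not a fixed property of the design. But four is the only ratio to which the protocol commits, and no finite ratio gives 1.48 on the stated inputs.

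Last, no planned decision depends on 1.48. The data already exist, and the reported interval will come from the actual counts. This limits the weight of the point.

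**Conclusion.** The point holds as a modest misstatement of precision. On the inputs of section 4.9.1, the planned crude odds ratio has an upper 95% limit of 1.55 at the 4:1 minimum, 1.54 at 5:1 and 1.51 at 10:1, against the stated 1.48. This rests on 50 expected cases in each group, a ratio of 1, Wald intervals, and controls whose exposure follows person-time.

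Three stronger readings are not supported:

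- *The study is not feasible or falls short.* The protocol expects more person-time than it assumes, and a moderate surplus offsets the cost of sampling controls.
- *1.48 requires 125,000 person-years in each group.* That holds only if the groups are equal, which the protocol does not require. About 167,000 non-user person-years with 100,000 in PPI current users gives the same limit.
- *Covariate adjustment, H2RA and the epilepsy strata make the figure worse still.* Adjustment usually widens an interval, but the documents give nothing from which to size this, and a crude figure is normal at planning. Silence on H2RA and on the epilepsy strata is an omission and not an error in the stated figure; section 4.9 calls the sub-analyses by epilepsy status descriptive.

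**What to change.** Restate section 4.9.1 for the planned analysis, for example: *with the same assumptions and four controls per case, the unadjusted 95% CI for the OR would extend to 1.55*. Keep the sentence that larger person-time is expected.

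If 1.48 is kept, either label it as the limit for a full-cohort rate ratio, or say that at 4:1 it needs more person-time than stated, with the two examples from step 4 of the working.

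The cost is one or two sentences and a slightly less favourable figure. Design, data collection and analysis do not change.
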